Participants in the intervention group will be invited to monitor their physical and emotional symptoms every day for 14-days using the Daily Record Keeping form (DRK; Boivin & Takefman, 1995), administered via JISC Online Surveys. **See Appendix 4 to view the daily DRK survey in Word document format. The online DRK survey can be viewed as it's presented on JISC Online Surveys via this link:** <https://southwales.onlinesurveys.ac.uk/daily-record-keeping-form-preview>. At 10am each day of the intervention period, participants in the intervention group will be sent an email asking them to complete the DRK survey by the end of the day- they will also receive text message reminders to complete the DRK at 5pm each day, unless they opt out of reminders. Both the email and text reminders will include a link to the online DRK. Participants can opt out of text message reminders at any time by emailing [name] requesting to opt out. Once participants have returned DRK surveys every day for 14 days, on the 15th day they will be asked to complete the follow-up survey within 24 hours. Once they have returned the follow-up survey they will be sent their £20 gift voucher via email. **See Appendix 5, page 1 to view a template of the daily DRK email reminders, see Appendix 5, page 2 to view a template of the text message reminders. See Appendix 6, page 1 to view the email template advising intervention group participants of their group allocation, and instructing them to complete the DRK survey each day for 14 days.** The online text messaging platform ClickSend will be used to manage the scheduling of daily text message (www.clicksend.com) See the section below titled "Data collection tools" for a more detailed explanation of the measures used in this study.

Control group:

Participants in the control group will not monitor their symptoms daily for 14-days and will instead be instructed to carry on as usual during the 2-week period, while the intervention group are monitoring. This group will complete all measures (including the DRK) at baseline and at follow-up on the 15th day only. **See Appendix 6, page 2 to view the email template advising control participants of their group allocation, and instructing them to carry on as usual for 14 days. If they indicated on the baseline survey that they are**

FACULTY OF LIFE SCIENCES AND EDUCATION FACULTY ETHICS SUB GROUP APPLICATION FORM

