9. MATERIALS AND METHODS

This study will use electronic means (online survey, email) and participants will receive a £20 Amazon voucher for completed participation. No face to face contact will occur between the research team and research participants. Participants will predominantly be recruited using JISC's online platform for connecting researchers with study participants (www.callforparticipants.com), as well as social media sites including Facebook and Instagram. Using these platforms, a research poster will be used to attract participants to the study and provide interested participants with a link to the screening questions, information sheet, consent form, and baseline survey. **See Appendix 7 to view the recruitment poster as it will be presented on www.callforparticipants.com, and shared on social media sites.**

The baseline survey (**see Appendix 1**) will collect the email addresses of interested participants. After submitting the baseline questionnaire, participants will be contacted via email with details about their group allocation and further instructions i.e. intervention participants will be instructed to complete 5-minute daily surveys each day for 14 days (see **Appendix 6, page 1** for instruction email template for intervention participants), whereas control group participants will be asked to continue as usual for 14 days (see **Appendix 6, page 2** for instruction email template for control participants). After the 14-day period both groups will be asked via email to complete the follow-up survey (**see Appendix 6, page 3**). The information sheet (**see Appendix 8**) and consent form (**see Appendix 9**) will precede the baseline survey and will provide full information about the nature of the study and details about what the participants in each group will be asked to do, including eligibility for the £20 incentive for taking part. The methodology for supplying participants with vouchers via email has been used in a previously approved study with no problems raised (ethics reference: 200401HR).

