There is a small risk that participants may use this mode of communication to consult [name] for help for physical or mental health problems, or they may disclose information which may require notification or follow up. To mitigate these risks, [name] will use a separate email address ([contact]) from her professional one to contact recruited participants, as agreed with USW IT. All emails sent from this email address will include a note at the end stating the following: *"Please do not reply to this email. If you would like to withdraw, please email [contact]. You can also email [contact] if you would like to opt out of text message reminders. If you have any questions or concerns about this study, please email: [REDACTED]"* It is anticipated that this instruction and the use of a study email address will minimise any chance of instantaneous nuisance replies to [name]. However, please note that [name] has not experienced any negative emails from participants in a recent menopause survey, so this is not anticipated in this study. The study email address will be used to advise recruited participants of their group allocation, their unique username, and provide further instructions (**see Appendix 6**). This email address will also be used to email a link to the DRK intervention to intervention group participants each day of the intervention period (**see Appendix 5 to view DRK link email template**), as well as a link to the follow-up survey to all participants (**see Appendix 6**). [name]'s personal USW email address will be provided on the information sheet (**Appendix 8**) and debrief forms (**see Appendix 12**) should participants have questions about the mechanics of completing the survey, it will be made clear on both forms that participants should only contact [name]'s email address for this purpose. If participants have any questions about anything else related to the survey such as the menopause, or concerns about the study, they will be directed to the Director of Studies ([name]) in the first instance. If participants have concerns or complaints that cannot be answered satisfactorily by [name] on consultation with the wider research team then the issue will be referred to the research governance officer: [name]. These contact details will be provided on the information and debrief sheets. It will also clearly be stated in the information sheet that the research team cannot provide medical advice and that any respondents who are concerned should contact their GP, and examples of help sources are made available to participants on the information and debrief sheets:

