27. PAYMENT TO RESEARCH PARTICIPANTS

Please note, participants should not be paid for taking risks. Payment should not be set to a level that would unduly influence potential participants. Information pertaining to participant payment should be included on the Participant Information Sheet.

Will participants be paid? YES

If yes, please give details.

All 78 participants will receive a £20 Amazon gift voucher. The £20 Amazon voucher will be emailed to respondents at the end of the 2-week research period pending they fully adhere to the instructions provided and do not withdraw. To adhere to the research instructions, all participants must fully complete the baseline and follow-up measures, and intervention participants must complete the DRK monitoring form each day for 14 days within 24 hours of receiving the links via email. All participants must complete the follow-up survey within 24 hours of receiving the link via email. This information will be provided on the information sheet, and the consent form will include items which will obtain confirmation that participants are aware that they must complete the requirements of the study in order to claim their Amazon voucher.

Some participants allocated into the control group may feel they would like to try the symptom monitoring intervention themselves. While it would be impractical to offer the exact intervention to control participants after the research period, a list of online symptom monitoring tools and mobile apps (e.g., Health and Her's online symptom tool, Clue's mobile app for period tracking) will be provided on the final debrief sheet which will be provided after the follow-up questionnaire is completed (**see Appendix 12, page 9 to view the follow-up debrief sheet, see this link: <https://southwales.onlinesurveys.ac.uk/follow-up-questionnaire-preview> to the follow-up survey which also presents the debrief sheet**).

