To be eligible for the £20 Amazon voucher, you must complete the follow-up survey within 24 hours of receiving the link via email.

Please do not reply to this email. If you would like to withdraw your data, please

email [contact]. You can also email [contact] if you would like to opt out of receiving text message reminders. If you have any questions or concerns about this study, please email: [REDACTED]

We thank you again for your participation,

The Research Team

The follow-up email template sent to participants after 14 days of either usual care or completing daily DRK surveys:

Hi,

You have now reached the end of the study; all you need to do now is complete the final follow-up survey (see the link below).

Your username is: **pilot1**

Please remember this username as it will be used to provide you with your £20 voucher, you can contact [contact] if you forget it.

You may open the **follow-up survey** in your web browser by clicking the link below:

**FACULTY OF LIFE SCIENCES AND EDUCATION
FACULTY ETHICS SUB GROUP APPLICATION FORM**

<https://southwales.onlinesurveys.ac.uk/follow-up-questionnaire-preview>

If the link above does not work, try copying this link into your web browser: <https://southwales.onlinesurveys.ac.uk/follow-up-questionnaire-preview>

This link is unique to you and should not be forwarded to others.

Once you have completed the follow-up survey you will be sent your **£20 Amazon gift voucher via email**, provided you have completed all surveys within the allocated time frames and have met the terms and conditions (see the information sheet attached for more information).

To be eligible for your £20 Amazon voucher, **you must complete the follow-up survey within 24 hours of receiving it**.

Please do not reply to this email. If you would like to withdraw your data, please email [contact]. You can also email [contact] if you would like to opt out of receiving text message reminders.

If you have any questions or concerns about this study, please email [REDACTED]

We thank you again for your participation,

The Research Team

**FACULTY OF LIFE SCIENCES AND EDUCATION
FACULTY ETHICS SUB GROUP APPLICATION FORM**

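### One missed daily form ends the payment for the day-15 outcome in the monitoring arm only, and the plan conflicts with itself on who is sent the follow-up survey

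*Combined protocol and SAP*

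**What the plan says.** **Who is asked for the day-15 outcome.** Section 8 (Intervention group) words the request as following a full set of daily forms: "Once participants have returned DRK surveys every day for 14 days, on the 15th day they will be asked to complete the follow-up survey". For controls the same section sets no such condition: "This group will complete all measures (including the DRK) at baseline and at follow-up on the 15th day only". Section 9 makes no distinction between arms: "After the 14-day period both groups will be asked via email to complete the follow-up survey". Section 15 describes the study email account as sending daily links to the monitoring arm, "as well as a link to the follow-up survey to all participants". Appendix 13 repeats that twice.

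**Who is paid.** Section 27 opens with "All 78 participants will receive a £20 Amazon gift voucher" and then makes payment depend on full adherence. For one arm, "intervention participants must complete the DRK monitoring form each day for 14 days within 24 hours of receiving the links via email". For both arms, "All participants must complete the follow-up survey within 24 hours of receiving the link via email". The daily email in Appendix 5 and the voucher terms in Appendix 14 repeat the all-14 condition. The follow-up email in Appendix 6 promises the voucher "provided you have completed all surveys within the allocated time frames". No partial payment is described.

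**Who is analysed.** Section 10 excludes anyone who does not complete every study material or does not comply fully. Section 14 keeps what drop-outs have already submitted, but section 22 gives no method for incomplete data.

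**The concern.** The main analysis (sections 8 and 22) is the group-by-time interaction on change from baseline to follow-up. Controls have no other post-baseline assessment. In the monitoring arm the daily DRK records symptoms, but section 8 keeps those records out of the analysis. Help-seeking, health anxiety, communication, decision-making, self-efficacy and health awareness are measured only at baseline and follow-up. A woman without a day-15 survey therefore contributes nothing to the planned comparison.

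A monitoring woman who misses or is late with one daily form has no voucher left to earn when the follow-up email arrives, and that email restates the condition she has failed. A control cannot lose the voucher through a missed form before day 15. The incentive to supply the outcome thus depends on behaviour that exists in only one arm. Section 7 of the protocol itself allows that monitoring may be taxing or harmful for some women, so missing forms could plausibly be related to how a woman responds. If it is, the women left in the two arms are no longer comparable, and no later choice of analysis can recover outcomes that were not collected.

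**Working it through.** **1. The plan's own allowance.** Section 10 needs 52 evaluable women (26 per arm) and allows 33% attrition: 52 / (1 − 0.33) = 77.6, rounded up to 78, or 39 per arm. This reproduces. The planned retention is 26/39 = 66.7%, so 13 of 39 may be lost in each arm. The same allowance is applied to both arms.

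**2. Timed tasks after baseline.** Monitoring arm: 14 daily forms + 1 follow-up = 15. Control arm: 1 follow-up. The voucher requires all of them on time.

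**3. Chance of keeping the voucher to day 15.** The documents give no on-time rate per form, so p is an assumption. With independent days, P(all 14 on time) = p^14, and expected forfeitures = 39 × (1 − p^14). Misses usually cluster in the same women, so the last column uses a beta-binomial model with an assumed within-woman correlation of 0.2. With s = 1/0.2 − 1 = 4 and a = 4p, P(all 14) is the product over i = 0 to 13 of (a + i)/(4 + i).

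| p (assumed) | p^14 | Forfeit, independent days | Forfeit, clustered |
|---|---|---|---|
| 0.99 | 0.869 | 5.1 | 2.4 |
| 0.98 | 0.754 | 9.6 | 4.7 |
| 0.97 | 0.653 | 13.5 | 6.9 |
| 0.95 | 0.488 | 20.0 | 10.9 |

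The matching count for controls is 0 of 39, because they have no daily forms. It says nothing about how many controls drop out.

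**4. Break-even.** If the all-14 condition did decide who counts, keeping 26 of 39 monitoring women would need p ≥ (26/39)^(1/14) = 0.971 under independence, before any other loss.

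**5. What selective loss could do.** Assume a normal model in which completing and symptom change have correlation ρ in both arms, and a fraction q is retained in each arm. The shift in the group difference is ρ × [φ(c₁)/q₁ − φ(c₀)/q₀], in SD of change, where c is the normal cut-off that leaves a fraction q. Take q₁ = 0.667 (the planned retention) and q₀ = 0.90 (the 10% internet attrition quoted in section 10). The bracket is 0.544 − 0.195 = 0.349. For ρ from 0.1 to 0.5 the shift is 0.035 to 0.175 SD. The sign follows the sign of ρ, which is unknown.

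**6. The definition of late.** Section 8 asks for the daily form by the end of the day. The text reminder in Appendix 5 allows until 10am the next morning, and section 27 allows 24 hours from the email. These must also be reconciled, because the voucher turns on them.

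**The case against.** The strongest reply is that section 8 only describes the normal sequence of events. Sections 9 and 15 and Appendix 13 send the survey to both groups or to everyone, section 8 itself has both groups completing follow-up, and no text says that the link is withheld from a woman who misses a form. That stands. A reader might infer from section 8 that such women are never asked for their outcome. The documents do not settle this; they contain a wording conflict.

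Other parts of the reply also stand:

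- A woman who has lost the voucher may still answer, so loss is a risk and not a stated consequence.
- One late form is not the same as stopping monitoring.
- Independence overstates forfeitures if misses cluster, as the last column of the table shows.
- The one-third attrition allowance, drawn partly from a study with a daily-monitoring arm, may cover the numbers.
- Paying for adherence to a daily task is a legitimate choice, and emails and text reminders support it.

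It is also tempting to say that the monitoring arm would look better than it is. That does not follow. The test is on change from baseline, so losing women with a heavier baseline burden does not by itself favour either arm, and women who improve might equally stop recording.

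What the reply does not remove is the difference between the arms. The attrition allowance covers numbers equal in both arms, not imbalance or selection. The voucher rule is clear, is repeated in four places, and bears on the day-15 outcome in one arm only.

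**Conclusion.** The point holds as a risk with two parts. First, section 8 conflicts with sections 9 and 15 and Appendix 13 on who is sent the follow-up survey, and they must be reconciled. Second, whichever reading is meant, the all-or-nothing voucher removes the payment for the day-15 outcome after one missed daily form, in the monitoring arm only. The main comparison could be biased if form completion is related to symptom change; the direction is not known.

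The size is illustrative. About 5 to 20 of 39 women would forfeit before day 15 at assumed on-time rates of 99% to 95% with independent days, or about 2 to 11 with the assumed clustering. A reader might take these as counts of missing outcomes; they are counts of forfeited vouchers. The 0.035 to 0.175 SD shift rests on assumed retention and correlation. The section 10 exclusion compounds the problem, because it would discard the outcomes of women who missed forms even if they were collected. The change should be made before recruitment, since the remedy is cheap and cannot be applied afterwards.

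**What to change.** 1. **Section 8.** State that on day 15 the follow-up link goes to every allocated woman, whatever number of daily forms she returned, and align this with sections 9 and 15 and Appendix 13. Use one definition of an on-time daily form in section 8, section 27 and Appendix 5. Cost: wording only.
2. **Section 27 and Appendices 5, 6 and 14.** Pay all of the voucher, or a fixed part of it, for baseline plus follow-up on the same terms in both arms. Only the remainder, if any, should depend on daily forms. Say in the follow-up email that the survey is still wanted and still paid if daily forms were missed. Cost: at most 78 × £20 = £1,560, which section 27 already commits. The downside is a slightly weaker incentive to return every daily form; a split payment limits this.
3. **Sections 10 and 22.** Analyse every woman with follow-up data in her allocated group regardless of daily-form completion, with full compliers as a sensitivity analysis. Without this, the outcomes gained by changes 1 and 2 would be thrown away. Report, by arm, how many women were sent the follow-up survey and how many returned it. Cost: wording and one extra analysis.
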